5.1 Inclusion Criteria

Subjects are eligible to be included in the study only if all of the following criteria apply:

All subjects:

- 101 Subject has provided informed consent prior to initiation of any study-specific activities/procedures.
- 103 Must be willing and able to undergo a core bone marrow biopsy (MM and AML subjects) and bone marrow aspirate (MM and AML subjects) at screening. Core bone marrow biopsy or bone marrow aspirate performed as prior SOC can be used to meet screening requirements if performed within 4 weeks from enrollment

and no curative anti-cancer therapy was administered during the time from biopsy to enrollment.

- 105 Eastern Cooperative Oncology Group (ECOG) performance status of 0 to 2
- 106 Age \geq 18 years old
 - For subjects in Japan only: if a subject is younger than 20 years at the time of signing the informed consent form, informed consent must be obtained from both the subject and his/her legal representative
- 107 Life expectancy of $>$ 3 months, in the opinion of the investigator
- 109 Hepatic function, as follows; total bile acid (TBA) $<$ 5 \times upper limit of normal (ULN), aspartate aminotransferase (AST) and alanine aminotransferase (ALT) \leq 3 \times ULN, total bilirubin \leq 1.5 \times ULN (except subjects with Gilbert's syndrome).
- 110 Cardiac function, as follows; left ventricular ejection fraction (LVEF) greater than or equal to 50%. 2-D transthoracic echocardiogram (ECHO) is the preferred method of evaluation. Multigated Acquisition Scan (MUGA) is acceptable if ECHO is not available.
- 111 Calculated or measured creatinine clearance (CrCl) of \geq 30 mL/minute calculated using the formula of Cockcroft and Gault $[(140 - \text{Age}) \times \text{Mass (kg)} / (72 \times \text{Creatinine mg/dL})]$. Multiply result by 0.85 if female.
- 112 Female subjects of childbearing potential must have a negative serum or urine pregnancy test within 3 days of the first dose (see Section 11.5 for definition of females of childbearing potential).

Multiple myeloma subjects only:

- 102 Pathologically documented, definitively diagnosed, MM relapse or refractory PD and have received at least 2 therapeutic treatments or regimens for MM. The investigator must be of the opinion that no other treatment option will result in a durable response.
- 104 Measurable disease per the International Myeloma Working Group (IMWG) response criteria (assessed within 28 days prior to enrollment), as indicated by one or more of the following:
 - Serum M-protein \geq 0.5 g/dL
 - Urine M-protein \geq 200 mg/24 hours
 - Subjects who do not meet 1 of the 2 prior criteria: serum free light chain (SFLC) $>$ 10 mg/dL (\geq 100 mg/L) and an abnormal SFLC ratio ($<$ 0.26 or $>$ 1.65) as per the IMWG response criteria
- 108 Hematological function, as follows without transfusion or growth factor support:
 - Absolute neutrophil count (ANC) \geq 1.0 \times 10⁹/L
 - Platelet count \geq 50X 10⁹/L (in subjects where $<$ 50% of bone marrow nucleated cells were plasma cells) or \geq 30 \times 10⁹/L (in subjects where \geq 50% of bone marrow nucleated cells were plasma cells) without transfusion or growth factor support
 - Subjects should not have received platelet transfusions for at least 1 week prior to screening

- Hemoglobin \geq 8 g/dL
- Screening ANC should be independent of granulocyte- and granulocyte/macrophage colony stimulating factor (G-CSF and GM-CSF) support for at least 1 week and of pegylated G-CSF for \geq 2 weeks

Acute myeloid leukemia subjects only:

- 113 AML as defined by the World Health Organization (WHO) Classification (Section 11.14) persisting or recurring following one or more treatment courses, and for subjects in Japan, determined by the investigator to be not eligible for approved anticancer drug therapy in Japan; EXCEPT acute promyelocytic leukemia (APL). The investigator must be of the opinion that no other treatment option will result in a durable response. In Part 5A cohorts 1 and 2, enrollment will be restricted to subjects with persisting or recurring AML after 1 to 2 lines of prior therapy.
- 114 Greater than or equal to 5% blasts (or blast equivalents) in bone marrow.
- 115 Circulating white blood cells (WBCs) $<$ 25 000/ μ L.

5.2 Exclusion Criteria

Subjects are excluded from the study if any of the following criteria apply:

All subjects:

- 201 Previously received an allogeneic stem cell transplant within 6 months OR having received immunosuppressive therapy within the last 3 months OR having signs or symptoms of acute or chronic graft-versus-host disease.
- 202 Autologous stem cell transplant less than 90 days prior to enrollment.
- 209 Currently receiving treatment in another investigational device or drug study. Other investigational procedures while participating in this study will be allowed if approved by Amgen medical monitor.
- 210 History of other malignancy within the past 2 years prior to enrollment, with the following exceptions:
- Malignancy treated with curative intent and with no known active disease present for \geq 2 years before enrollment and felt to be at low risk for recurrence by the treating physician
 - Adequately treated non-melanoma skin cancer or lentigo maligna without evidence of disease
 - Adequately treated cervical carcinoma in situ without evidence of disease
 - Adequately treated breast ductal carcinoma in situ without evidence of disease
 - Prostatic intraepithelial neoplasia without evidence of prostate cancer
 - Adequately treated urothelial papillary noninvasive carcinoma or carcinoma in situ
- 211 Known sensitivity to any of the products or component to be administered during dosing.

- 212 Myocardial infarction within 6 months of enrollment, symptomatic congestive heart failure (New York Heart Association > class II).
- 213 History of arterial thrombosis (eg, stroke or transient ischemic attack) in the past 6 months prior to enrollment.
- 214 Active infection requiring IV anti-infective treatments within 1 week of enrollment
- 215 Known or suspected human immunodeficiency virus (HIV) infection or subjects who are HIV seropositive. Testing will be performed if required by local regulatory authorities.
- 216 Exclusion of hepatitis B and C infection based on the following results:
- Positive for hepatitis B surface antigen (HbsAg) (indicative of chronic hepatitis B or recent acute hepatitis B)
 - Negative HbsAg and positive for hepatitis B core antibody (HbcAb) and/or hepatitis B surface antibody (HBsAb; Japan only): hepatitis B virus DNA by polymerase chain reaction (PCR) is necessary. Detectable hepatitis B virus DNA suggests occult hepatitis B. Negative for PCR test can be enrolled in the study
 - Positive Hepatitis C virus antibody (HCVAb): hepatitis C virus RNA by PCR is necessary. Detectable hepatitis C virus RNA suggests chronic hepatitis C. Negative for PCR test can be enrolled in the study
- 217 Unresolved toxicities from prior anti-tumor therapy, defined as not having resolved to Common Terminology Criteria for Adverse Events (CTCAE) version 4.0 grade 1, or to levels dictated in the eligibility criteria with the exception of grade 2 peripheral neuropathy, alopecia or toxicities from prior anti-tumor therapy that are considered irreversible (defined as having been present and stable for > 4 weeks may be allowed if they are not otherwise described in the exclusion criteria AND there is agreement to allow by both the investigator and sponsor).
- 218 Treatment with medications known to cause QT interval corrected (QTc) interval prolongation within 1 week prior to enrollment unless approved by the Amgen Medical Team.
- 219 Anti-tumor therapy: chemotherapy, antibody therapy, molecular targeted therapy, or investigational agent within 5 times the $t_{1/2}$ of the drug, or until the relevant biological effect has resolved (whichever is longer). Exceptions: hydroxyurea to control peripheral blood leukemic cell counts is allowed until prior to receiving the first dose of AMG 176. Hydroxyurea is unapproved for AML in Japan.
- 220 Prior systemic radiation therapy must have been completed at least 28 days prior to enrollment. Prior focal radiotherapy completed at 14 days prior to enrollment.
- 221 Major surgery within 28 days of enrollment.
- 235 Women of reproductive potential who are unwilling to practice an acceptable method of highly effective birth control while on study through 3 months after receiving the last dose of study drug. Men who are unwilling to practice sexual abstinence (refrain from heterosexual intercourse) or use a condom with spermicide during treatment and for an additional 4 months following the last dose of study drug if sexually active with a female of childbearing potential. For acceptable methods of highly effective birth control, and definition of females of childbearing potential see Section 11.5.

- 223 Women planning to become pregnant or breastfeed while on study through 3 months after receiving the last dose of study drug. Subjects who suspend breastfeeding prior to starting treatment with study drug and do not intend to resume breastfeeding before 3 months after receiving the last dose of study drug can be enrolled
- 236 Male subjects who are unwilling to abstain from donating sperm during treatment and for an additional 4 months following the last study drug administration
- 224 History or evidence of any other clinically significant disorder, condition or disease that, in the opinion of the investigator or Amgen physician, if consulted, would pose a risk to subject safety or interfere with the study evaluation, procedures or completion.
- 225 Use of any medications (except anti-tumor medications), including herbal medicines (eg, St. John's wort), vitamins, or supplements consumed by the subject within 5 times the $t_{1/2}$ of the drug, or until the relevant biological effect has resolved (whichever is longer), and continuing use if applicable, that was not reviewed and approved by the principal investigator and the Amgen medical monitor prior to enrollment. Written documentation of this review and Amgen acknowledgment is required for subject participation.
- 226 Use of known strong inhibitors of CYP3A4 within 5 times the $t_{1/2}$ or until the relevant biological effect has resolved (whichever is longer), prior to enrollment unless reviewed and approved by the principal investigator and the Amgen medical monitor prior to enrollment. Written documentation of this review is required for subject participation. Exception: use of azole antifungal therapies falling into this category based on the current data from Part 3d subjects.
- 228 Use of known CYP3A4 sensitive substrates with a narrow therapeutic window within 5 times the $t_{1/2}$ of the drug or its major active metabolite or until the relevant biological effect has resolved (whichever is longer), following the last dose of the drug prior to receiving the first dose of AMG 176 unless reviewed and approved by the principal investigator and the Amgen medical monitor prior to enrollment. Written documentation of this review and Amgen acknowledgment is required for subject participation. Refer to prescribing information for any concomitant medications
- 229 Use of known OATP1B1 and/or OATP1B3 or BCRP substrates with a narrow therapeutic window within 5 times the $t_{1/2}$ of the drug or its major active metabolite or until the relevant biological effect has resolved (whichever is longer), following the last dose of the drug prior to enrollment unless reviewed and approved by the principal investigator and the Amgen medical monitor prior to enrollment. Written documentation of this review and Amgen acknowledgment is required for subject participation. Refer to prescribing information for any concomitant medications.
- 230 Subject likely to not be available to complete all protocol required study visits or procedures, and/or to comply with all required study procedures (eg, Patient Reported Outcomes) to the best of the subject and investigator's knowledge.
- 231 Subjects with elevated cardiac troponin above the manufacturer's 99th percentile upper reference limit (URL) for ADVIA Centaur XP assay (0.04 ng/mL for females and 0.059 ng/mL for males) at screening confirmed by the central laboratory.
- 232 Subjects with evidence of recent cardiac injury at screening based on creatine kinase-muscle/brain (CK-MB), N-terminal prohormone of brain natriuretic peptide (NT-pro-BNP), and electrocardiogram (ECG) assessments at screening.

- 239 DDI assessment cohort with itraconazole only: History of QT prolongation, torsades de pointes, ventricular tachycardia, and cardiac arrest
- 240 History or evidence of severe acute respiratory syndrome coronavirus 2 (SARS-CoV-2) infection unless agreed upon with medical monitor and meeting the following criteria:
- negative test for SARS-CoV-2 RNA by real time polymerase chain reaction (RT-PCR) within 72 hours prior to first dose of AMG 176; and
 - no acute symptoms of coronavirus disease 2019 (COVID-19) within 10 days prior to first dose of AMG 176 (counted from day of positive test for asymptomatic subjects)
- 241 Prior treatment with an MCL1 inhibitor.

Multiple myeloma subjects only:

- 203 Multiple myeloma with IgM subtype.
- 204 POEMS syndrome (polyneuropathy, organomegaly, endocrinopathy, monoclonal protein, and skin changes).
- 205 Existing plasma cell leukemia or rapidly proliferating extra medullary disease unless discussed and approved by Amgen medical monitor prior to enrollment.
- 206 Waldenstrom's macroglobulinemia.
- 207 Amyloidosis.
- 208 Glucocorticoid therapy (prednisone > 30 mg/day or equivalent) within 7 days prior to enrollment. Topical or inhaled corticosteroids are permitted.

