4.3.1.2.3 Part 3d

For AML Part 3d, the dose selected is 60 mg/m² (IV, QW), which was selected based on considerations of the predicted magnitude of the DDI during co-administration with itraconazole and available safety and efficacy data.

Itraconazole is widely used as a strong index inhibitor of CYP3A4 in clinical DDI studies based on potency and specificity of CYP3A4 inhibition and is also a clinical inhibitor for P-gp (Chen et al, 2019; Liu et al, 2016; US FDA, 2016). Patients with AML are susceptible to invasive fungal infections and often require prophylaxis and treatment with antifungal agents such as voriconazole and posaconazole (Halpern et al, 2015; Lat and Thompson, 2011), which are known to inhibit CYP3A4 and P-gp. AMG 176 is metabolized, in part, by CYP3A4, and is a P-gp substrate; hence, co-administration with inhibitors of CYP3A4/P-gp may lead to increases in AMG 176 exposure. As a result, clinical trials with AMG 176 previously prohibited the use of medications that are strong CYP3A4/P-gp inhibitors, including voriconazole and posaconazole.

A DDI assessment is planned in a separate cohort of AML subjects (Part 3d) in the FIH study 20150161 to evaluate the effect of itraconazole, a strong CYP3A4 and P-gp inhibitor, on the pharmacokinetics of AMG 176. In Part 3d, subjects receive oral itraconazole capsules (200 mg) QD starting at 8 am on day -3 through day 4 (total of 7 days) to achieve adequate CYP3A4/P-gp inhibition prior to, and following, AMG 176 administration. AMG 176 is dosed QW on day 1 of week 1 through 3. Data analysis is conducted to assess AMG 176 exposure changes with or without co-administration of itraconazole (exposures on week 1 vs week 3).

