6.1.7 Excluded Treatments, Medical Devices, and/or Procedures During Study Period

The following medications and/or therapies should not be administered within the timeframes specified prior to enrollment or during the study (unless otherwise specified below):

- Allogenic stem cell transplant

- Autologous stem cell transplant
- Anti-tumor therapy (chemotherapy, antibody therapy, molecular targeted therapy, retinoid therapy, or investigational agent or procedures); concurrent use of bisphosphonates or denosumab for bone loss are permitted. In subjects with AML hydroxyurea is allowed to control blasts as described in Section [6.7.2](#).
- NOTE: Hydroxyurea is unapproved for AML in Japan.
- Treatment with medications known to cause QTc interval prolongation unless approved by the Amgen Medical Team
- Any live vaccine therapies used for the prevention of infectious disease
- Any major surgery or radiotherapy unless agreed upon by Amgen and investigator
- Over the counter medication(s) that was not reviewed and approved by the principal investigator and the Amgen medical monitor
- Herbal medicines (eg, St. John's wort) that were not reviewed and approved by the principal investigator and the Amgen medical monitor

The use of certain medications and illicit drugs within 5 half-lives or 28 days, whichever is shorter prior to the first dose of study drug and for the duration of the trial will not be allowed. If a prohibited medication is required for single use (such as for a procedure) while study drug is held, the Amgen medical monitor can approve such use.

The following medications or non-drug therapies are prohibited:

- Use of known strong inhibitors of CYP3A4/P-gp such as ketoconazole, itraconazole, HIV protease inhibitors, nefazodone, cyclosporine, erythromycin, clindamycin, tetracycline, and clarithromycin within the 14 days or 5 times the $t_{1/2}$ of the drug, or until the relevant biological effect has resolved (whichever is longer); or products containing grapefruit, Seville oranges, or St. John's wort within 7 days, prior to enrollment. Exception: use of azole antifungal therapies.
- Use of known CYP3A4 sensitive substrates with a narrow therapeutic window (such as pimozide, and sirolimus) within 5 half-lives of the drug or its major active metabolite, whichever is longer, following the last dose of the drug prior to receiving the first dose of AMG 176. Refer to prescribing information for concomitant medications.

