6.1.8 Concomitant Medications with Itraconazole (Part 3d only)

Itraconazole has the potential to interact with many concomitant drugs. Please refer to the current itraconazole US Prescribing Information (USPI) for additional information including:

- Medications which are contraindicated and prohibited during and after the last dose of itraconazole administration
- Medications which are not recommended during and after the last dose of itraconazole administration
- The following medications are contraindicated with itraconazole and should not be administered during concomitant administration with itraconazole: cisapride, oral midazolam, nisoldipine, pimozide, quinidine, dofetilide, triazolam, levacetylmethadol (levomethadol), and ergot alkaloids such as dihydroergotamine, ergometrine (ergonovine), ergotamine, and methylergometrine (methylergonovine). This is not an exhaustive list; please refer to itraconazole USPI for additional details.

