6.7.2.2 Antifungal Prophylaxis

Use of micafungin (or other echinocandins), posaconazole (or other azole antifungals), and amphotericin B for antifungal prophylaxis is allowed for neutropenic subjects with AML.

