9.4.2.4 Other Analyses

9.4.2.4.1 Pharmacokinetic Analyses

The analysis of pharmacokinetic endpoints will include data from all subjects who have received at least 1 dose of the investigational product and have at least 1 pharmacokinetic sample collected.

The PK parameters for AMG 176 including, but not limited to C_{max} , minimum observed concentration (C_{min}), AUC, CL, and, if feasible, $t_{1/2}$ will be estimated using standard non-compartmental PK methods and summarized by dose groups using means, standard deviations, medians, minimums, and maximums for intensive and peak/trough determinations. AMG 176 concentrations at each time point along with PK parameter values may be reviewed for each subject. Individual AMG 176 concentration/time profiles will be plotted by dose groups. Summary statistics will be computed for each sampling time and parameter as appropriate. For subjects in Part 3d (DDI assessment with itraconazole), AMG 176 PK parameters (C_{max} , AUC) will be compared from day 1 (with itraconazole) to day 15 (without itraconazole) to evaluate the effect of itraconazole on the PK of AMG 176. Geometric mean ratios for C_{max} and AUC values and associated 90% CI (Test/Reference) will be estimated. The “Test” treatment will be AMG 176 co-administered with itraconazole on day 1, while the “Reference” treatment will be AMG 176 administered without itraconazole on day 15. Analysis of the relationship between AMG 176 dose and exposure parameters (AUC and C_{max}) will be conducted and plots of the relationship between AMG 176 dose and exposure parameters along with dose proportionality assessment will be provided. Additional analyses to explore relationship between exposure and safety and exposure and efficacy may also be performed. Pharmacokinetic parameters such as C_{max} , AUC, and $t_{1/2}$, if feasible, will be estimated and summarized for azacitidine.

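### The azole antifungal permissions carry no Part 3d exception, so the day 15 reference of the interaction analysis may contain another CYP3A4/P-gp inhibitor

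*Protocol*

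**What the plan says.** **The comparison.** Protocol Section 3 gives Part 3d one primary objective: the PK of AMG 176 alone and with itraconazole. Section 9.4.2.4.1 takes day 1 as test. The reference is "AMG 176 administered without itraconazole on day 15", and the planned summary is: "Geometric mean ratios for C_{max} and AUC values and associated 90% CI (Test/Reference) will be estimated". The reference is thus defined by the absence of one drug, not by the absence of CYP3A4/P-gp inhibition.

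**The azole permissions.**
- Section 5.2, criterion 226, is listed for all subjects and governs use before enrollment. It ends: "Exception: use of azole antifungal therapies falling into this category based on the current data from Part 3d subjects".
- Section 6.1.7, on prohibited medication, ends its strong-inhibitor item with: "Exception: use of azole antifungal therapies".
- Section 6.7.2.2 says: "Use of micafungin (or other echinocandins), posaconazole (or other azole antifungals), and amphotericin B for antifungal prophylaxis is allowed for neutropenic subjects with AML".

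None of the three sets Part 3d apart.

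**Text specific to Part 3d.** Criterion 239 concerns QT and arrhythmia history. Section 6.1.8 deals with drugs that must not be combined with itraconazole ("The following medications are contraindicated with itraconazole and should not be administered during concomitant administration with itraconazole"). It names no other azole and says nothing about the day 15 profile.

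**Analysis rules.** The PK Analysis Set (Protocol Section 9.3.1; SAP Section 6.5) can drop data affected by major protocol deviations. SAP Section 13 places the interaction assessment outside the SAP.

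**The concern.** Section 4.3.1.2.3 names posaconazole and voriconazole as inhibitors of CYP3A4 and P-gp, the pathways that itraconazole is used to block. Study itraconazole stops on day 4. A neutropenic Part 3d subject who then starts posaconazole could still be taking it on day 15. That profile would meet the written definition of the reference and yet not be AMG 176 alone.

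Because the use is permitted, it is not a deviation, and the PK Analysis Set rule would not remove the pair. An inhibitor in the reference raises reference exposure and lowers the test/reference ratio. If the true ratio is above 1, as the PBPK model in Section 4.3.1.2.3.1 predicts, the estimate moves toward no interaction. At stake is Part 3d's only primary objective. Section 4.3.1.2.3 also promises further analysis as data from up to 11 subjects arrive, and the later subjects are the ones to whom the permission applies.

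**Working it through.** **Inputs**
- True ratio R: the PBPK-predicted AUC ratio, 1.2 to 1.4 (Section 4.3.1.2.3.1). It cannot be rebuilt, because the model inputs are not in the documents. It is taken as given.
- n = 11, the approximate size of Part 3d (Section 4.1.3). No power calculation is given for the interaction.
- k: the number of subjects on another azole at day 15 but not at day 1. Not in the documents; assumed.
- g: the log-scale effect of that azole relative to itraconazole. Not in the documents. Section 2.1 chose itraconazole so that its result could be extended to other azoles, which corresponds to g = 1.
- Timing: 5 subjects had data in November 2022 (Section 4.3.1.2.3). The azole exclusion was lifted by Amendment 15, dated 09 February 2023. If those 5 were treated under the earlier prohibition, k is at most about 11 − 5 = 6.

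**Formula**

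An unaffected pair has expected log ratio ln R. An affected pair has ln R − g ln R. Averaging over n pairs:

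expected ratio = R^(1 − g × k/n)

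**Results**

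| k of 11 | g | exponent | R = 1.2 | R = 1.4 |
|---|---|---|---|---|
| 0 | any | 1 | 1.20 | 1.40 |
| 3 | 1 | 8/11 | 1.14 | 1.28 |
| 6 | 0.5 | 8/11 | 1.14 | 1.28 |
| 6 | 1 | 5/11 | 1.09 | 1.17 |
| 6 | 1.5 | 2/11 | 1.03 | 1.06 |

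The first row returns the protocol's own prediction. For k = 6 and g = 1 the expected reading falls by 1.200 − 1.086 = 0.114 at the lower prediction and by 1.400 − 1.165 = 0.235 at the upper one. The formula does not cover a subject who takes another azole on both days. That case depends on how two inhibitors combine, on which the documents give no figure.

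**Scale.** The preliminary ratios in Section 4.3.1.2.3 are 0.62 for Cmax (90% CI 0.15, 1.10) and 0.79 for AUC from 0 to 168 hours (90% CI 0.24, 1.33). The AUC interval spans 1.33 − 0.24 = 1.09, far more than the shifts above.

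**The case against.** **Medication is reviewed.** Criterion 225 excludes subjects using medication, including continuing use, that the investigator and medical monitor have not approved in writing. Section 8.1.1 sends the medication list to the medical monitor at consent and asks both to approve new drugs before they start. An azole would therefore come to the sponsor's attention. This stands as a practical safeguard, but neither passage tells the approver to keep the Part 3d reference free of azoles, and three other passages permit them.

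**Voriconazole is not clearly permitted.** Appendix 11 lists it among QTc-prolonging drugs prohibited on study, with ciprofloxacin as the only exception. Section 6.7.2.2 allows other azoles, and Section 6.1.7 lets the sponsor's medical team approve QTc drugs. These passages conflict. Posaconazole is not on the Appendix 11 list, so the point rests on it.

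**Criterion 226 concerns use before enrollment.** True. The permission that reaches day 15 comes from Sections 6.1.7 and 6.7.2.2.

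**The shift is small against the noise.** This also stands. The preliminary ratios are already below 1, and a bias of the illustrated size may not be visible in about 11 subjects.

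**A stronger reading is tempting:** that the exception is circular, or that azoles were opened to Parts 4 and 5 on contaminated data. The documents do not support it. The clinical data behind the change were reported in November 2022, before Amendment 15, and Section 4.3.1.2.3 says that strong CYP3A4/P-gp inhibitors, with both azoles named, had previously been prohibited. PBPK modeling also supported the change. Later exposure cannot have biased a decision already taken.

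**Conclusion.** The gap is real. As written, the plan allows another CYP3A4/P-gp inhibitor in a reference period that is meant to show AMG 176 alone, and no analysis rule would identify or remove such a pair. The direction of the bias rests on the protocol's premise that azoles act alike and on a true ratio above 1. The reading of about 1.09 to 1.17 instead of 1.2 to 1.4 is an illustration, with 6 of 11 pairs affected and equal inhibition. Half the relative inhibition gives 1.14 to 1.28.

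A reader might infer that Part 3d's result is in fact contaminated. The documents do not show that. They do not say how many subjects enrolled after Amendment 15 or whether any took an azole, and the medication review may have prevented it. SAP Section 10 also states that the study was terminated early, so an eligibility change may protect no one. The interaction comparison is not on that section's list of dropped analyses, so how exposed pairs are handled still matters for any collected after Amendment 15.

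**What to change.** 1. **Reconcile the text.** Bring criterion 226, Sections 6.1.7 and 6.7.2.2 and Appendix 11 into line with each other and with the Part 3d objective. Which antifungal rule applies to Part 3d subjects is a clinical decision for the sponsor.
2. **Define the reference and the primary estimate.** In Section 9.4.2.4.1, or in the document that will govern the interaction analysis, define the reference profile as free of strong CYP3A4/P-gp inhibitors. Compute the primary geometric mean ratios and 90% CIs without pairs exposed to another such inhibitor through the last day 15 profile sample (168 hours, day 22). Report the all-pairs result as a sensitivity analysis, with the number of pairs excluded.

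No new data are needed: Section 6.7.2 already collects drug name, dose and start and stop dates from screening to 30 days after the last dose.

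The cost is precision. If 6 of 11 pairs left the primary estimate, its log-scale standard error would rise by a factor of √(11/5) ≈ 1.48 at unchanged variability, and the interval would widen. If no pair was exposed, nothing changes.
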